10. STATISTICAL CONSIDERATIONS

10.1 Study Endpoints, Analysis Sets, and Covariates

10.1.1 Study Endpoints

10.1.1.1 Primary Endpoints

Phase 1b:

- Incidence of DLT

Phase 3:

- Progression-free Survival by blinded independent central review using modified RECIST (PFS): Time from randomization to the date of disease progression (response evaluation by blinded independent central review using modified RECIST 1.1) or death, whichever occurs earlier.
- Overall Survival (OS): Time from randomization date to the date of death from any cause.

10.1.1.2 Secondary Endpoints

Phase 1b:

- Confirmed ORR (CR+PR) (response evaluation by investigator using modified irRC).
- BOR, DRR (duration of response for 6 months or longer), DOR (the time from date of the initial confirmed response to the date of the first documented PD or death), DCR, and PFS (response evaluation by investigator using modified irRC).
- OS.
- Incidence of treatment-emergent and treatment-related adverse events (all AEs, grade ≥ 3 AEs, SAEs, fatal AEs, AEs defined as events of interest), and abnormal laboratory tests.

Phase 3:

- iCRR by blinded independent central review using modified irRC-RECIST
- iPFS by blinded independent central review using modified irRC-RECIST
- OS in subjects excluding stage IVM1c per CRF
- ORR (CR + PR), BOR, DRR, DOR (the time from date of the initial confirmed response to the date of the first documented PD or death), and DCR (response evaluation by blinded independent central review using modified RECIST 1.1), and iORR (iCR + iPR), iBOR, iDRR, iDOR, and iDCR response evaluation by blinded independent central review using modified irRC-RECIST).
- Incidence of treatment-emergent and treatment-related adverse events (all AEs, grade ≥ 3 AEs, SAEs, fatal AEs, and AEs defined as events of interest), and abnormal laboratory tests.
- Changes in EORTC QLQ-C30 GHS/QoL subscale.

10.1.1.3 Exploratory Endpoints

[REDACTED]

- iORR (iCR + iPR), iBOR, iDRR, iDOR, and iPFS (response evaluation by investigator using modified irRC-RECIST).

[REDACTED]

- Changes in the EORTC QLQ-C30 subscales.
- **Changes in HSU estimates derived via EQ-5D-3L.**

[REDACTED]

- Incidence of anti-pembrolizumab antibodies.
- Descriptive statistics of trough and peak levels of pembrolizumab (MK-3475).

[REDACTED]

10.1.2 Analysis Sets

DLT Analysis Set

The DLT analysis set will include DLT-evaluable subjects enrolled in phase 1b who have had the opportunity to be on treatment for at least 6 weeks from the initial dosing of

[figure not shown]
pembrolizumab and received at least 2 doses of talimogene laherparepvec and 2 doses of pembrolizumab in combination (ie, on the same day) or otherwise experienced a DLT within 6 weeks after starting the combination therapy.

Full Analysis Set

The primary analysis of all efficacy endpoints for phase 3 part of the study, unless noted otherwise, will be conducted on the full analysis set defined as all randomized subjects. All subjects will be analyzed according to treatment to which they are randomized.

Safety Analysis Set

The safety analysis set will include all subjects who received at least 1 dose of talimogene laherparepvec or pembrolizumab. The safety analysis set will be defined separately for the phase 1b and phase 3. For phase 3 all subjects will be analyzed according to the treatment they received.

Approved

PRO Population

The PRO population includes the subset of the subjects in the full analysis set who had received at least 1 dose of study therapy and had at least 1 PRO assessment. A PRO assessment will be defined as completed if at least 1 subscale/domain can be calculated from the questionnaire. Patient reported outcome populations will be defined separately for each questionnaire (EORTC QLQ-C30 and EQ-5D-3L) and for the secondary endpoint of EORTC QLQ-C30 GHS/QoL.

10.1.3 Covariates and Subgroups

Randomization will be stratified by stage of disease: less advanced stages (IIIB, IIIC, and IVM1a) versus more advanced stages (IVM1b and IVM1c) and by prior BRAF inhibitor therapy: no prior BRAF inhibitor versus prior BRAF inhibitor with or without MEK inhibitor.

[figure not shown]
The following baseline covariates and randomization stratification factors may be used to examine efficacy in subgroups or in multivariate analyses:

[figure not shown]
- Region, if applicable (USA or non-USA)
- Age: < 50, ≥ 50; < 65, ≥ 65; < 75, ≥ 75 years
- Individual disease stage: IIIB vs IIIC vs IVM1a vs IVM1b vs IVM1c
- Grouped disease stage: IIIB/C-IVM1a vs IVM1b/c (CRF and IVRS)
- Grouped disease stage: IIIB/C-IVM1b vs IVM1c
- LDH: ≤ ULN vs > ULN
- Sex (female vs male)
- ECOG performance status (0 vs 1)
- HSV-1 serostatus (positive vs negative)
- The sum of longest, or shortest for nodal, diameters of target lesions (SLD) **determined by blinded independent central review (will be dichotomized based on median)**
- **Baseline PD-L1 status (positive vs not positive)**
- Prior BRAF inhibitor (none vs BRAF inhibitor alone vs BRAF and MEK inhibitors in combination): if subjects included in each of the 2 BRAF related category represent ≥ 10% of the study population (CRF)
- Prior BRAF inhibitor (yes versus no BRAF inhibitor with or without MEK inhibitors) (IVRS)
- **Baseline of BRAF^{V600} mutation: yes vs no vs missing/unknown**

10.2 Sample Size Considerations

10.2.1 Sample Size Considerations for Phase 1b

Six to nine DLT-evaluable subjects will be required to assess the DLT profile of talimogene laherparepvec in combination with pembrolizumab for phase 1b. The sample size of approximately 6 to 9 subjects is determined empirically and is consistent with those used in 6+3 phase 1 designs to evaluate the safety of a single dose of each agent assuming a true incidence rate of DLT is 11 to 33%. Additional subjects, up to a total of 20, will be enrolled in the phase 1b portion of the trial to address the secondary objective exploring the relationship between [REDACTED] and response to treatment.

[figure not shown]

10.2.2 Sample Size Considerations for Phase 3

There are 2 primary endpoints for phase 3, PFS and OS. A 1/3 reduction in hazard ratio (talimogene laherparepvec with pembrolizumab / placebo with pembrolizumab) for PFS (HR = 0.67), and a hazard ratio of 0.70 for OS are hypothesized in the Full Analysis Set. Assuming events follow piece-wise exponential distributions (Figure 1 and Figure 2), the hypothesized HRs will translate into a relative increase of 167% in median PFS time and 44% in median OS time. The absolute increase in median PFS will be 9.4 months (5.6 to 15.0 months) in the talimogene laherparepvec and placebo arm and 12.4 months (28 to 40.4 months) in median OS.

[figure not shown]
Approved

Figure 1. Progression-free Survival

Median PFS (pembrolizumab), 5.6 months; $p(t)$ = event rate at month t ; $p(1.5) = 0.95$; $p(3) = 0.6$; $p(6) = 0.49$; $p(12) = 0.39$; $p(18) = 0.32$; $p(24) = 0.30$; constant hazard in each interval between 2 consecutive pieces; a constant hazard ratio across all pieces.

Figure 2. Overall Survival

Median OS (pembrolizumab) = 28 months; $p(t)$ = event rate at month t ; $p(48) = 0.31$ and $p(60) = 0.27$; constant hazard in each interval between 2 consecutive pieces; a constant hazard ratio across all pieces.

The overall Type I error for the dual primary endpoints is 2-sided 0.05. The event goal for PFS to achieve 90% power at 2-sided 0.005 is 407 and that for OS to achieve 90% power at a 2-sided 0.045 is 346 after taking into account the group-sequential interim OS analyses. The OS event goal is not adjusted for the non-binding OS futility assessment at the second OS interim analysis. The sample size is 660 (ie, 330 per arm) based on an estimate of 346 death events occurring within 5 years (60 months) with approximately 48% of subjects censored. Assuming a non-uniform subject accrual rate for which 50% of cumulative enrollment is accrued at 2/3 of expected total enrollment period (Lachin and Foulkes, 1986), and exponential distributions for loss to follow up for PFS and OS with an annual rate of 5% for OS and 10% for PFS, Table 9 displays estimated timing of analysis based on the actual enrollment rate:

Table 9. Timing of Primary Analysis for PFS (at 407 events) and OS (at 346 events)

Enrollment Duration (month)	PFS PA DCO (month)	OS Events (% event goal) at PFS PA DCO	OS PA DCO (month)
26	48	252 (73%)	75

DCO = data cutoff at event goal; OS = overall survival; PA = primary analysis; PFS₁ = progression free survival per blinded independent central review using modified RECIST 1.1.

Analysis timings are further informed by event projection simulations based on KEYNOTE-006 year 4 data for all subjects in the pembrolizumab arm. Analysis timings assume the hypothesized constant hazard ratio of 0.67 for PFS and 0.70 for OS (see Table 10 below).

[figure not shown]
In addition to hypothesis tests for the dual primary endpoints, statistical tests of the secondary endpoints, iCRR and iPFS, by blinded independent central review using

modified irRC-RECIST, and OS in the disease subgroup excluding IVM1c, will be performed. [Table 10](#) shows event goals (or analysis time) based on hypothesized effect sizes and simulated powers for testing 5 endpoints, where PFS and iPFS refer to the modified RECIST 1.1 and modified irRC-RECIST criterion, respectively. The simulated powers are based on the Maurer-Bretz graphic-based multiple testing procedure ([Maurer and Bretz, 2013](#)) assuming a 1-time analysis. Details of the multiple testing procedure are described in [Section 10.5](#).

Table 10. Hypothesized Effect Sizes and Hypothesis Test Powers

Hypothesis	Effect Size	Primary Analysis Timing	Simulated Power ^a
H ₁ (OS)	HR = 0.70	346 events	91%
H ₂ (PFS)	HR = 0.67	407 events	90%
H ₃ (iPFS)	HR = 0.60	256 events	94%
H ₄ (iCRR)	OR = 3.9	DCO for PFS PA	97%
H ₅ (OS subgroup)	HR = 0.60	Earlier of 208 events or 5 years minimum follow-up	90%

DCO = data cutoff at event goal; H = hypothesis; HR = hazard ratio; iCRR = complete response rate (by modified irRC-RECIST); iPFS = progression free survival (by modified irRC-RECIST); OR = odds ratio; OS = overall survival; PA = primary analysis; PFS = progression free survival

A CRR (95% CI) of 24% (8-47), per modified irRC, was observed in phase 1b subjects of the study with 36 weeks minimum follow-up time ([Long et al, 2016](#)). It is also reported that CRR in pembrolizumab, per RECIST, was 5% (3-8) from KEYNOTE-006 ([Joseph et al, 2014](#)) and 3% (1-10), per irRC, from KEYNOTE-001 ([Robert et al, 2015](#)). Assuming 6% CRR in pembrolizumab and 20% in the combination arm, then the odds ratio of 3.9 is hypothesized for iCRR in the phase 3 part of the study.

10.3 Access to Individual Subject Treatment Assignments by Amgen or Designees

To guard against actual or perceived bias due to subjective decisions made by Amgen or Designee in light of potentially unblinding data captured during phase 3 of the study, the study team will comply with Amgen standard operating procedures that govern restricted and potential unblinding data access. Subject-level unblinding data will be available to an external independent biostatistics group that supports the DMC safety and efficacy reviews. The external DMC will be the primary reviewer of the unblinding results for interim safety, efficacy, and futility analyses prior to the primary analysis of OS (see [Section 10.4.3](#)). If the DMC recommends to stop the study due to safety concerns

or declares that an efficacy or futility criterion has been met, then the sponsor may unblind a restricted study team as deemed necessary.

Unblinding and potentially unblinding information for subjects and investigators should not occur prior to the study being unblinded for the primary analysis of OS except as specified (eg, [Section 5.2](#), [Section 9.2.1.2](#), and [Section 10.4.3](#)).

10.4 Planned Analyses

10.4.1 Interim Analyses

A DLT interim safety analysis was planned and conducted by the study team for phase 1b. Data were reviewed by a DLRT.

All analyses prior to the primary OS analysis will be conducted by an external independent biostatistics group and reviewed by the DMC per the DMC charter. The analyses will include safety monitoring, ORR/DCR and OS futility, primary and possibly interim PFS₁, and interim OS analyses. The study team is responsible for conducting the primary analysis of OS and all subsequent analyses.

10.4.1.1 DLT Safety Analysis (Phase 1b)

An interim safety analysis in phase 1b to evaluate DLT included 6 subjects who were eligible for DLT evaluation (see [Section 10.1.2](#) for definition of DLT-evaluable subjects in the DLT Analysis Set). Data were reviewed by a DLRT as summarized in [Section 3.1.1.1](#). Rules for determination of DLTs are described in [Section 3.1.1.1](#).

10.4.1.2 Interim Safety Analysis (Phase 3)

Planned safety monitoring in phase 3 will first occur after approximately 20 and 100 subjects, respectively, have been enrolled in phase 3 and have had an opportunity to be followed for at least 6 weeks after receiving study treatment and approximately every 6 months after the DMC meeting for the futility analysis for ORR and DCR has been completed until the later of the study team's unblinding or the primary analysis of OS. Monitoring guidelines for futility will be provided to the DMC. Additional ad hoc safety and/or efficacy data reviews may be requested by the DMC as needed.

10.4.1.3 Interim iORR and iDCR Futility Analysis (Phase 3)

An interim futility analysis of iORR and iDCR per blinded independent central review using modified irRC-RECIST is planned to include the first 160 subjects (ie, approximately 80 per arm) that have had a chance to be followed for the tumor assessment scheduled at week 24. The analysis will include the first 160 subjects enrolled. All tumor response data will be included up to 26 weeks from the date of first dose of study therapy for the 160th enrolled subject (or randomization date if subject is not dosed). The futility criterion will be based on the Bayesian method.

Beta (8.75, 16.25) and Beta (12.5, 12.5) prior distributions are assumed for the true placebo plus pembrolizumab arm (arm 2) iORR and iDCR in the trial population with means equal to 0.35 and 0.50, respectively, and both with the precision equal to a sample size of 25. Beta (10.08, 10.92) and (14.91, 6.09) prior distributions are assumed for the iORR and iDCR for the combination of pembrolizumab and talimogene laherparepvec (arm 1) with means equal to 0.48 and 0.71, respectively, and both with a concentration parameter of 21. The priors for the combination correspond to the results from a 24-week minimum follow-up analysis of the 21 subjects in the phase 1b part of the study.

Beta posterior distributions for the iORR and iDCR will be calculated for each arm based on the corresponding prior distribution and the observed study iORR and iDCR results. The iORR futility criterion will be a posterior probability < 0.65 of at least a 6% absolute iORR increase (Arm 1 – Arm 2), and the iDCR futility criterion will be a posterior probability < 0.75 of at least a 10% absolute iDCR increase. The DMC will declare the combination therapy futile if both the iORR and iDCR futility criteria are met; however, the DMC's recommendation will be non-binding and therefore the sponsor will make the final decision to terminate the study prematurely.

10.4.1.4 Interim Efficacy and Futility Analysis (Phase 3)

There are **5** planned analysis time points for hypothesis testing, including primary and/or interim analyses of the 5 hypotheses (H): H₁, associated with OS; H₂, PFS by blinded independent central review assessed modified RECIST 1.1; H₃, iPFS by blinded independent central review assessed modified irRC-RECIST; H₄, iCRR by blinded independent central review assessed modified irRC-RECIST; and H₅, OS subgroup excluding IVM1c (Table 10). The analysis times are defined by the following event-driven time points with the DMC responsible for Analyses #1, #2, and #3.

1. **OS interim analysis and PFS primary analysis at 407 PFS events (DMC).**
2. OS interim analysis at 282 events (including a futility analysis) (DMC).
3. **OS interim analysis at 315 events (DMC).**
4. OS primary analysis at 346 events.
5. OS subgroup primary analysis at earlier of 208 events in subgroup or 5 years minimum follow-up.

Note that there is no sequential order in these **5** analysis times (with the exception that Analysis #2 is before Analysis #3, and Analysis #3 before Analysis #4). Each analysis time may also include interim or primary analyses for the other endpoints. Endpoints to be analyzed, and the type of analysis (ie, interim or primary), are presented in Table 11 and are dependent on which hypotheses have been rejected. For example, testing for

iCRR and iPFS at an analysis time point will be conditional upon previously rejecting either H_1 or H_2 . O'Brien-Fleming group sequential boundaries based on the Lan-DeMets approach (O'Brien and Fleming, 1979) will be used for testing endpoints with interim analyses. Multiple testing procedures will utilize the graphic-based Maurer-Bretz approach (Section 10.5).

The information fractions will be based on the events included at the time of analysis for testing of all time to event endpoint null hypotheses (ie, H_1 , H_2 , H_3 , and H_5) and it will be based on the number of subjects with potential follow-up time of at least 36 weeks for testing the iCRR null hypothesis (ie, H_4). The maximum information for testing iCRR is all randomized subjects. Each analysis time will have a corresponding database snapshot; however, there will not be a separate snapshot for each endpoint tested at the same analysis time.

1. The initial alpha allocation for testing the hypothesis of PFS (H_2) is 0.5% and 4.5% for OS (H_1). There will not be a nominal alpha passed back to H_2 after rejecting H_1 or other hypotheses at any analysis.
2. An interim OS analysis will be performed at Analysis #1 with all death events, regardless if H_2 is rejected. In the event when Analysis #2 occurs prior to Analysis #1, then it will include an interim analysis to test H_2 for PFS (using all PFS events) and, if H_2 is not rejected, it will be tested again at the planned time for Analysis #1. However, if the projected time for achieving 407 PFS events is within 4 months from the projected 282 OS events time, then Analysis #2 will be combined with Analysis #1 and be performed at Analysis #1 using all death events with PFS times censored after the 407th PFS event.
3. At each of the 5 planned analysis times, it will be considered an interim analysis of iCRR and iPFS, rather than the primary analysis, if the maximum information has not been reached for the respective endpoint at that time. For example, if H_3 is tested in an analysis that includes fewer than 256 iPFS events, then it will be an interim analysis of iPFS that includes all observed events; otherwise, it will be the primary analysis with all iPFS times censored after the date of the 256th event. If all randomized subjects do not have at least 36 weeks follow-up in an analysis, then it will be an interim analysis for iCRR only including those subjects with at least 36 weeks follow-up; otherwise, it will be the primary analysis and include all randomized subjects. With the exception of PFS, the hypothesis for an endpoint may be re-tested after its primary analysis using its primary analysis data if alpha is subsequently propagated to it from the rejection of another hypothesis.
4. Assuming Analysis #1 is before Analysis #2, and at Analysis #1 the null hypothesis of PFS (H_2) is rejected, the hypotheses H_3 and H_4 will be tested. H_1 will be tested at Analysis #1 regardless of whether H_2 is rejected. The iPFS (H_3) and iCRR (H_4) can be tested if H_2 is not rejected but H_1 is significant. Likewise, OS subgroup (H_5) can be tested at Analysis #1 if any of the following set of hypotheses are rejected: (1) H_2 and H_3 ; (2) H_2 and H_4 ; (3) H_1 and H_3 ; or (4) H_1 and H_4 .

Approved

5. If projections indicate 256 iPFS events will occur in the same timeframe as either Analysis #1 or Analysis #2, then the option will be considered to extend the data cutoff to include all 256 iPFS events. In this event, Analysis #1 will have PFS times censored after the 407th PFS event and Analysis #1 or #2 will include all OS events.
6. The OS hypothesis (H_1) will be tested at Analyses #1-4 with all (Analysis #1) or required number (Analysis #2, Analysis #3, and Analysis #4) of events in the absence of its prior rejection (or futility at Analysis #2).
7. The OS subgroup hypothesis (H_5) will be tested at the first and all subsequent analysis times when alpha can be propagated to it from the rejection of H_1 or H_2 followed by H_3 and/or H_4 . All OS events in the subgroup at the end of 5 years follow-up will be used if 208 events have not been observed. If H_1 is not rejected by Analysis #4, it will be tested again using events at Analysis #4 if alpha can be propagated from the rejection of H_5 at Analysis #5.
8. Likewise, H_3 and H_4 may be re-tested if not rejected by their primary analysis using their respective primary analysis data if H_1 is subsequently rejected.

Table 11 illustrates possible hypothesis tests at the 5 planned analyses.

Table 11. Study Analyses and Possible Hypothesis Tests

Analysis	Timing	Hypothesis Tested (Analysis Type)				
		H_1 (OS)	H_2 (PFS)	H_3 (iPFS)	H_4 (iCRR)	H_5 (OS subgroup)
#1	407 PFS events	(IA)	(PA)	If reject H_1 or H_2 (IA if < 256 events)	If reject H_1 or H_2 (IA if includes fewer than all random-ized)	If reject H_2 and either H_3 or H_4 , or reject H_1 and either H_3 or H_4 (IA if < 208 events)
#2	282 OS events	(IA)	n/a (IA if Analysis #2 is performed first)	If reject H_1 or H_2 (PA on first 256 events)	If reject H_1 or H_2 (PA if includes all random-ized)	If reject H_2 and either H_3 or H_4 , or reject H_1 and either H_3 or H_4 (IA if < 208 events)
#3	315 OS events	(IA)	n/a	If reject H_1 or H_2 (PA on first 256 events)	If reject H_1 or H_2 (PA if includes all randomized)	If reject H_2 and either H_3 or H_4 , or reject H_1 and either H_3 or H_4 (IA if < 208 events)
#4	346 OS events	(PA)	n/a	See Analysis #2 and #3 above	See Analysis #2 and #3 above	See Analysis #2 and #3 above

Footnotes defined on next page of table

Page 1 of 2

Approved

Table 11. Study Analyses and Possible Hypothesis Tests

Analysis	Timing	Hypothesis Tested (Analysis Type)				
		H ₁ (OS)	H ₂ (PFS)	H ₃ (iPFS)	H ₄ (iCRR)	H ₅ (OS subgroup)
#5	Earlier of 208 OS events in subgroup or 5 years minimum follow-up	If reject H ₂ previously and H ₅ (PA at first 346 events)	n/a	See Analysis #2 and #3 above	See Analysis #2 and #3 above	See Analysis #2 and #3 above (PA)

Page 2 of 2

H = hypothesis; IA = interim analysis; iCRR = complete response rate (by modified irRC-RECIST); iPFS = progression free survival (by modified irRC-RECIST); n/a = not applicable; OS = overall survival; PA = primary analysis; PFS = progression free survival

Futility Analysis for OS

At the 282 OS events interim analysis (ie, Analysis #2), if hypothesis H₁ is not rejected, then an OS futility analysis will be evaluated by the DMC. The interim OS futility analysis will be non-binding and define futility as a conditional power < 10% assuming a constant treatment effect (Denne, 2001); the corresponding OS futility boundary is 0.89, assuming a constant HR = 0.70. OS futility will also be evaluated by the DMC considering a possible non-constant treatment effect that increases over time (eg, a 2-interval model with a cutpoint between 4-8 months and constant treatment effect in each interval, where the second interval has a larger effect than the first one). To limit the probability of futility < 0.02, the futility boundary for the observed HR at 282 OS events analysis will be 0.93. Guidelines for this possible late effect will be provided in the DMC charter amendment. Operating characteristics of the primary analysis of PFS and sequential tests of OS are shown in Table 12 based on the OS events expected at Analysis #1.

Approved

Table 12. Analysis Timing, Nominal Significance Levels, and Boundary Properties

Analysis	Data cut-off (mon)	Endpoint (scenario)	Event (% goal)	Efficacy nominal 2-sided α	Futile HR ^b	Prob. Futile ^b		Efficacy HR	Power total
						H ₀	H ₁		
PFS PA	48	PFS	407 (100)	0.0050				0.76	90%
OS IA ₁	48	OS (PFS-)	252 (73)^a	0.0150				0.74	66%
		OS (PFS+)		0.0173				0.74	67%
OS IA ₂	52	OS (PFS-)	282 (82)	0.0187	0.89	84%	2%	0.76	76%
		OS (PFS+)		0.0212	0.89	83%	2%	0.76	77%
OS IA₃	61	OS (PFS-)	315 (91)	0.0261				0.78	84%
		OS (PFS+)		0.0292				0.78	85%
OS PA	75	OS (PFS-)	346 (100)	0.0336				0.80	90%
		OS (PFS+)		0.0372				0.80	90%

IA = interim analysis; H₀ = null hypothesis; H₁ = alternative hypothesis; HR = hazard ratio; OS = overall survival; PFS = progression free survival; PA = primary analysis. O'Brien-Fleming spending α for OS; futility if conditional power < 10%; H₀: HR = 1 and H₁: HR = 0.67 (PFS) and 0.70 (OS). Testing OS at an overall 2-sided 0.045 if PFS is not significant at 2-sided 0.005 (eg, PFS-); testing OS at 0.05 when all other null hypotheses are rejected (eg, PFS+).

^a The events for OS IA₁ are not pre-determined; the estimates shown are the number expected at the time of PFS PA.

^b The futile HR and probabilities are shown for the conditional power criterion only which assumes a constant OS effect.

Approved

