10.5.1 Multiple Hypothesis Testing Procedures and Multiplicity Adjustment

Multiple statistical hypothesis tests will be conducted which include testing for primary endpoints of PFS and OS and the 3 secondary endpoints (iCRR, iPFS, and OS in the subgroup excluding disease stage IVM1c) at multiple analysis time points. To control the study-level overall Type I error, a graphic-based multiple testing procedure for group sequential tests for multiple endpoints will be utilized (Maurer and Bretz, 2013). No updated information will be used when a hypothesis is re-tested at a later time point after its primary analysis. A hypothesis can be re-tested repeatedly with a different nominal level that is propagated from rejecting other hypothesis test(s). The following figure illustrates the Maurer-Bretz multiple testing procedure with initial 2-sided α allocation specified as a fraction used for each hypothesis test. Each hypothesis is represented by a circle. A 0 fraction in the circle indicates a hypothesis that is tested conditional on rejection of another hypothesis. The fractions in the square on the directed arrows connecting 2 hypotheses indicate the proportion of α propagated to the next hypothesis test(s) when the current hypothesis is rejected.

Approved

Figure 3. Initial Graph of Maurer-Bretz Multiple Testing Procedure

$$H_1 \alpha = 0.05 \times 9/10 = 0.045$$
$$H_2 \alpha = 0.05 \times 1/10 = 0.005$$

Due to the nature of Maurer-Bretz multiple testing procedure, the range of nominal levels used for hypothesis tests of OS is between 4.5% and 5%, and nominal levels used for testing the OS subgroup can range between 0.05% to 5%.

Further details regarding the derivation of nominal significance levels for each hypothesis test at the planned analyses will be provided in the Statistical Analysis Plan.

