$w_i(\cdot)$	-	-	-	-	1/10
$w_i(\cdot)\alpha$	-	-	-	-	0.005
$\alpha_{i,1}^*(w_i(\cdot)\alpha)$	-	-	-	-	0.0015
Rejected: OS, iPFS; ^Rejected: PFS, iCRR			Test: OS subgroup		
$w_i(\cdot)$	-	-	-	-	9/125
$w_i(\cdot)\alpha$	-	-	-	-	0.0036
$\alpha_{i,1}^*(w_i(\cdot)\alpha)$	-	-	-	-	0.0010
Rejected: OS, iCRR; ^Rejected: PFS, iPFS			Test: OS subgroup		
$w_i(\cdot)$	-	-	-	-	9/500
$w_i(\cdot)\alpha$	-	-	-	-	0.0009
$\alpha_{i,1}^*(w_i(\cdot)\alpha)$	-	-	-	-	0.0002
Rejected: PFS, iPFS; ^Rejected: OS, iCRR			Test: OS subgroup		
$w_i(\cdot)$	-	-	-	-	9/1000
$w_i(\cdot)\alpha$	-	-	-	-	0.00045
$\alpha_{i,1}^*(w_i(\cdot)\alpha)$	-	-	-	-	0.0001
Rejected: PFS, iCRR; ^Rejected: OS, iPFS			Test: OS subgroup		
$w_i(\cdot)$	-	-	-	-	1/1000
$w_i(\cdot)\alpha$	-	-	-	-	0.00005
$\alpha_{i,1}^*(w_i(\cdot)\alpha)$	-	-	-	-	0.000005
Rejected: PFS, iPFS, iCRR, OS subgroup; ^Rejected: OS			Re-test: OS		
$w_i(\cdot)$	1	-	-	-	-
$w_i(\cdot)\alpha$	0.05	-	-	-	-
$\alpha_{i,1}^*(w_i(\cdot)\alpha)$	0.0173	-	-	-	-
Rejected: PFS, iPFS, OS subgroup; ^Rejected: OS					
$w_i(\cdot)$	0.909	-	-	-	-
$w_i(\cdot)\alpha$	0.04545	-	-	-	-
$\alpha_{i,1}^*(w_i(\cdot)\alpha)$	0.0152	-	-	-	-

Table 5. Example 2-sided Nominal Significance Levels at the OS Interim Analysis 1 or PFS PA (ie, 407 PFS) With Partial or Full Information for All Remaining Hypotheses

	OS	PFS	iPFS	iCRR	OS Subgroup
Rejected: PFS, iCRR, OS subgroup; ^Rejected: OS					
$w_i(\cdot)$	0.901	-	-	-	-
$w_i(\cdot)\alpha$	0.04505	-	-	-	-
$\alpha_{i,1}^*(w_i(\cdot)\alpha)$	0.0150	-	-	-	-

Page 5 of 5

Table 6 provides an example of testing 5 endpoints at the time of PFS PA assuming the observed information fractions are: **252/346** for OS, 100% for PFS, iPFS, and iCRR, and 168/208 for OS subgroup and observed nominal p-values are 0.03 for OS, 0.001 for PFS, 0.003 for iPFS, 0.011 for iCRR, and 0.01 for OS subgroup. Because $p_{2,1}$ (PFS endpoint) is less than 0.005, the PFS endpoint is significant and therefore, the two secondary endpoints (iPFS and iCRR) can be tested. Regardless of what happens to iCRR, because $p_{3,1}$ is less than 0.0040, which is the significance level for iPFS when only PFS is significant, this endpoint is significant. Because both PFS and iPFS are significant, iCRR is tested at 0.00455, which is not significant, and OS subgroup is tested at 0.0001, which is not significant.

Table 6. Example of Nominal P-values and Significance Levels at PFS PA

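### Minor: the OS futility cells, the lower limit of the OS-subgroup alpha and one iPFS level do not agree with the plan's own tables

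*Protocol*

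**What the plan says.** **OS futility.** Protocol 10.4.1.4 and SAP 8.1.4 "define futility as a conditional power < 10% assuming a constant treatment effect", tested at 282 deaths if OS is not already significant, and add that "the corresponding OS futility boundary is 0.89, assuming a constant HR = 0.70". Protocol Table 12 and SAP Table 4 then print, at the 282-death look:

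| Scenario | Futile HR | P(futile), H0 | P(futile), H1 | Final OS level, same table |
|---|---|---|---|---|
| PFS- (overall 0.045) | 0.89 | 84% | 2% | 0.0336 |
| PFS+ (overall 0.05) | 0.89 | 83% | 2% | 0.0372 |

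Footnote b to Table 12 states the basis: "The futile HR and probabilities are shown for the conditional power criterion only which assumes a constant OS effect".

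**OS-subgroup alpha.** Protocol 10.5.1 and SAP 10.5.1.1 say that "nominal levels used for testing the OS subgroup can range between 0.05% to 5"%. The same Protocol sentence says that "the range of nominal levels used for hypothesis tests of OS is between 4.5% and 5"%. In SAP Appendix B, Table 5, the row headed "Rejected: PFS, iCRR; ^Rejected: OS, iPFS" allocates 0.00005 to the OS subgroup.

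**iPFS level.** The worked example before Table 6 in SAP Appendix B says the iPFS p-value "is less than 0.0040, which is the significance level for iPFS when only PFS is significant". Table 5 and Table 6 both print 0.0045 for that case.

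**The concern.** A conditional-power boundary depends on the critical value at the final analysis. If the final level becomes stricter, conditional power at a given interim HR falls, and the 10% point moves to a lower HR. The futility cells should therefore follow from the 0.0336 and 0.0372 printed in the same table. If they do not, the DMC reads an HR and stopping probabilities that belong to a slightly different rule from the one it is asked to apply.

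The other two items are plainer. The text states significance levels that differ from the table that derives them. Rounding is no excuse for an allocated alpha, because a test is judged against it directly.

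**Working it through.** **Inputs.** Deaths at the four OS looks: 252 (expected), 282, 315 and 346. Overall OS alpha 0.045 (PFS-) or 0.05 (PFS+). Lan-DeMets O'Brien-Fleming spending, 1:1 randomization, design HR 0.70 (Protocol 10.4.1.4, Table 12; SAP Appendix B).

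**The efficacy side reproduces.** Integrating the spending function at 252/282/315/346 gives nominal levels of 0.0150, 0.0187, 0.0261, 0.0336 and 0.0173, 0.0212, 0.0292, 0.0372. These match Table 12 exactly. The efficacy HRs also agree to two decimals (for PFS-: 0.7361, 0.7558, 0.7783, 0.7957, printed 0.74, 0.76, 0.78, 0.80). The model is therefore the sponsor's.

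**(a) Futility cells.** On the score scale:

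- Score needed at 346 deaths: z_f × √346 / 2.
- Score at 282 deaths: −ln(HR) × 282 / 4.
- Increment over the last 64 deaths under HR 0.70: mean 0.3567 × 64 / 4 = 5.707, SD √(64/4) = 4.
- Conditional power is 10% when the increment still needed is 5.707 + 1.2816 × 4 = 10.833.
- Given the boundary HR, P(futile) = Φ(z) under H0 and Φ(z − 0.3567 × √282 / 2) under H1, with z = −ln(HR) × √282 / 2.

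| | PFS- | PFS+ |
|---|---|---|
| Final level; z_f | 0.0336; 2.1248 | 0.0372; 2.0836 |
| Score needed at 346 | 19.762 | 19.378 |
| Score at 282 for 10% (less 10.833) | 8.929 | 8.545 |
| HR = exp(−4 × score / 282) | **0.881** | **0.886** |
| P(futile), H0 | **85.6%** (printed 84%) | **84.6%** (printed 83%) |
| P(futile), H1 | **2.7%** (printed 2%) | 2.4% (printed 2%) |

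Nearest rounding does not rescue the PFS- HR. At 0.885, the lowest HR that rounds to 0.89, conditional power is already 8.7%; at 0.89 it is 7.2%. For PFS+, 0.89 and 2% are correct and only 83% is off.

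Read backwards, a printed 84% (83.5% to 84.5%) needs a final level of 0.0374 to 0.0409, and a printed 83% needs 0.0409 to 0.0446. The table has 0.0336 and 0.0372. Recomputing the current schedule without the 315-death look (252/282/346) gives final levels of 0.0376 and 0.0416, HRs of 0.886 and 0.891, 84.4% and 83.3% under H0, and 2.4% and 2.1% under H1. All six printed cells then match. This is consistent with futility cells that were not refreshed for the 315-death look, but the mismatch stands whatever its cause.

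**(b) OS-subgroup alpha.** From the Table 5 weights:

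- PFS and iCRR rejected, OS and iPFS not: 1/1000 × 0.05 = 0.00005 = 0.005%.
- PFS and iPFS rejected, OS and iCRR not: 9/1000 × 0.05 = 0.00045 = 0.045%.

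Both are below 0.05%, the first by a factor of ten. The stated range must mean allocated alpha, because the 4.5% to 5% given for OS in the same Protocol sentence cannot be nominal levels: those run from 0.0150 to 0.0372 in Table 12. Reading it as nominal would not help, since Table 5 gives 0.000005 for the smallest path at 168 of 208 deaths.

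**(c) iPFS level.** With only PFS rejected, 9/100 × 0.05 = 0.0045. The example assumes 100% iPFS information, so interim spending cannot bring this down to 0.0040.

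**The case against.** The best defence of the PFS- row is that its boundary was rounded toward the side where the rule holds. At HR 0.88 conditional power is 10.4%, so the rule is not met; at 0.89 it is 7.2%, so it is. At exactly 0.89, P(futile) is 83.6% under H0 and 2.2% under H1, which round to the printed 84% and 2%. On this reading a printed 0.88 would be an HR at which the criterion fails.

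The reading does not survive the PFS+ row. Both rows print 0.89, so if the probabilities were evaluated there, both would show 84% under H0; the table shows 84% and 83%. Table 12 also rounds its efficacy HRs to nearest (0.7361 to 0.74, 0.7957 to 0.80), not to the side where the criterion is met. What does stand is that 0.88 must be labelled an approximation to the conditional-power rule.

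A second objection is that the documents cite a paper for conditional power and print no formula. Other conventions were tried with the current design. Allowing a crossing at 315 deaths leaves the HRs at 0.881 and 0.886. Freedman's drift gives 0.880 and 85.8% for PFS-. Using the current trend gives 0.844 and 0.848, and using the unadjusted final alpha gives 0.895 and 0.900. None returns the printed row.

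On (b), 0.045% could be said to round to 0.05%; 0.005% cannot. On (c), the slip is in a hypothetical example, and Table 6 just below it prints the right value. It is also fair that conditional power, not the printed HR, defines futility, and that the DMC separately considers a late-effect boundary of 0.93, which is not questioned here.

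**Conclusion.** The concern holds on all three items and is minor.

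- **PFS- futility:** HR off by 0.009, P(futile) by 1.6 points under H0 and 0.7 points under H1. An observed HR between 0.881 and 0.89 has probability 2.0% under H0 and 0.5% under H1. The error is against stopping.
- **PFS+ futility:** one cell, 83% where 84.6% follows.
- **OS-subgroup lower limit:** ten times too high.
- **iPFS level:** 0.0005 too low; the example's p = 0.003 is significant at either value.

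Type I error is unaffected, because futility is non-binding and Table 5 carries the correct alphas. Item (a) assumes the usual normal approximation for the log-rank statistic with 1:1 allocation, the expected 252 deaths at the first OS look, and conditional power against the final boundary under HR 0.70. Items (b) and (c) need only the printed weights.

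**What to change.** 1. In Protocol Table 12 and SAP Table 4, restate the 282-death futility cells as 0.88, 86%, 3% (PFS-) and 0.89, 85%, 2% (PFS+).
2. In Protocol 10.4.1.4 and SAP 8.1.4, say the boundary is about 0.88 (PFS-) or 0.89 (PFS+), and that it approximates the governing conditional-power rule, which is computed from the actual deaths and the actual final critical value.
3. In Protocol 10.5.1 and SAP 10.5.1.1, change the lower limit for the OS subgroup from 0.05% to 0.005%.
4. In the SAP Appendix B worked example, change 0.0040 to 0.0045.

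The cost is a few table cells and three short text corrections. Efficacy boundaries, event goals and type I error do not change.
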